participants in the consent form) within the course of approximately 10 months and separated by an intermediate “washout” period of 4 months (Figure 1). Subject will not be required to refrain from fish or seafood during this washout period. Prior to the second trial subjects will receive a commercially available over the counter prebiotic (Prebiotin™) to be orally self-administered on a regular schedule for the entire trial 2 period. This prebiotic is not the subject of this investigation in this study, and is simply selected for its known effects of shifting gut microbial composition to enrich for healthier strains of bacteria (e.g. Bifidobacteria). Fecal sampling prior to and subsequent to prebiotic will be used to document changes in the microbiota for each individual. The prediction is that prebiotic induced change in the gut microbiota will result in a change in MeHg metabolism kinetics in each

individual.

2B. Rationale for Study Design

The main rationale for this study design is based on our evidence that de-methylation of MeHg in the human gut is the driving force for faster elimination MeHg that comes with eating fish. We therefore predict that with the methods we now have available to measure MeHg kinetics, coupled that with high-resolution analyses of gut microbiome characteristics in individual people who have undergone a controlled exposure to MeHg, we can resolve a microbial basis for MeHg metabolism in humans. This is an ambitious undertaking, and hence, is designed as a consortium project to be executed by three investigators with respective expertise in 1) human MeHg kinetics, 2) mouse microbiome manipulations and 3) microbial metagenomics and culturing methods. By design, the human subject component of the study is to be carried out at URMC. The objective is to capture “slow” and “fast” MeHg metabolizing human microbiome samples, that can be handed off to colleagues at MSU for specialized analyses that do not involve the human subjects, simply their de-identified samples.

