Information collected from the subjects at the initial study visit will be: age, sex, body weight, presence/absence of dental amalgams and medications currently taken. This will be collected without the need to access medical records. Subjects will be provided with a notebook carrying templates to fill in for a food diary. Alternatively, subjects who currently use a personal food tracking application (e.g. "My Fitness Pal" or "Healthwatch 360") can substitute a print out from this application of their food consumption record for period spanning the trial.

Fish meal administration. Just prior to each trial, individually weighed, wrapped and frozen portions of tuna steaks in 6-8 oz (170-227gm) portions will be prepared by and purchased from a local market (Wegman's). Portions will be kept frozen in a dedicated freezer in the P.I.'s lab until the time of distribution to the subjects. Frozen fish portions will keep over the time of distribution to enrolling participants (~ 2-3 months, <https://stilltasty.com/fooditems/index/18559>). Tuna portions will be prepared from one large fish fillet, so subjects will be receiving portions from the same fish within each Trial. A sample of the fish tissue will be set aside at the time of purchase to determine mercury content in the fish. Mercury measurements will be performed at the URMC EHSC Elemental Analysis Facility. Fish mercury values will be used to calculate predicted exposures to subjects based on individual body weights (see 9B, Protection

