Hair sample collection and submission. Hair samples will be collected during a visit of the subject to the P.I.'s laboratory on approximately day 74 (60 days after the last fish meal). Sampling within a five-day window of this target time will be acceptable. Hair will be sampled manually by direct withdrawal from the scalp. Sampling from the posterior region of the head will be done for all the subjects. Direct withdrawal of three

to five strands at once is found to elicit little discomfort and yield root material that can be used as a reference landmark for the start of the LA-ICP-MS analysis. A total of 20-25 hair strands will be collected for each subject and stored in a zip-lock bag. Hairs will then be mounted on double stick tape on a microscope slide and stored at room temperature until LA-ICP-MS analyses (see below). Hair samples will also be logged-in and coded for identity protection in the P.I.'s laboratory.

Food and health diary. Subjects will be requested to keep a food diary for the periods spanning each of the 75 days of Trial 1 and 2. The diary is to include a list of types of food eaten and drinks consumed at each meal. Careful accounting of amounts of food or caloric intake will not be requested. In addition, subjects will be asked to record incidents of illness (e.g. cold or flu) or stresses (e.g. work or personal) that are likely to contribute to unusual eating patterns, digestive distress or metabolic imbalance. A food diary will not be requested for the intervening 4-month washout period. However, participants, at the visit prior to Trial 2, will be asked to comment on fish/seafood eating frequency and if illness or undue stress was experienced during the washout period.

Analytical procedures.

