6. CONCOMITANT AND DISALLOWED MEDICATIONS

Administration of antibiotic medication within two months prior to the study is an exclusion criterion. Antibiotic administration during the elimination period of the 75 day of protocol will not be disallowed, however, but must be reported to the P.I. No additional treatments or alteration of concomitant medication schedules will be necessary.

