11. DATA ANALYSIS AND MONITORING

Sample Size Determination

We will target 40 participants (20 women, 20 men)for the reason that some statistical power is expected while we also are aiming to keep the study size appropriate for the logistics of recruiting and retention of subjects for both trials. We aim to recruit and consent 46 participant (23 women, 23 men) in anticipation of some drop out. A

complete cohort of 20 women and 20 men will afford the opportunity to assess sex-based differences. We have performed power analysis on the pairwise correlations between k_{el} and MeHg demethylation rate and/or bacterial taxa abundance. With grouped sexes, 40 subjects will have at least 80% power to detect a linear relationship where 19% or more of the variance in elimination rate is explained by de-methylation status or particular bacterial species abundance.

Planned Statistical Analysis

Relationships of taxa abundance with kinetic parameters of MeHg elimination rate (k_{el}), biotransformation in vivo (B_{vivo} , %iHg in feces) and in vitro (B_{vitro} , %MeHg biotransformation in cultures) will be evaluated. A total of 117 numerical values for k_{el} and B_{vivo} , B_{vitro} will be available (37 from our prior study and 40 subjects X 2 trials in the present study). Evaluation of slopes and R^2 values for elimination rate calculations in the prior study demonstrates that a difference of two days in MeHg half-life between two subjects can be determined with significance. Pairwise t-tests will be used to assess significance among pre- vs. post-prebiotic elimination rates (Aim1). The correlation between the (k_{el}) and biotransformation (B_{vivo} and B_{vitro}) will be evaluated for the 40 X 2 = 80 new human subject determinations in Aim 1. Graphical and numerical diagnostics will be used to test the linearity of the relationships and the homogeneity of variance. If these conditions are met, linear regression will be used to estimate functions for predicting k_{el} from B_{vivo} or B_{vitro} . The R system for statistical computing will be used throughout [26].

Data and Safety Monitoring.

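### Pre-trial history is taken differently before the two compared trials: medicines and antibiotics only before Trial 1; fish intake, illness and stress only before Trial 2

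*Combined protocol and SAP*

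**What the plan says.** **Before Trial 1.** Section 5C (Subject recruitment and subject information) gives the items taken at the initial visit: "age, sex, body weight, presence/absence of dental amalgams and medications currently taken". Fish intake, recent illness and stress are not among them. Section 3B excludes people who used antibiotics in the two months before the study. The phone screen in Section 4A also asks about antibiotics, with a one-month look-back. Its fish question concerns allergy, not consumption.

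**Before Trial 2.** Section 5C (Food and health diary) states that "participants, at the visit prior to Trial 2, will be asked to comment on fish/seafood eating frequency". The same visit covers illness and stress since Trial 1. It mentions neither medicines nor antibiotics, and Appendix 1 adds no such item. Section 2A leaves diet free in between: "Subject will not be required to refrain from fish or seafood during this washout period". No diary is kept in the washout.

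**Within each trial.** The diary covers food, illness and stress in both trials. Section 6 allows antibiotics in the elimination period but says that their use "must be reported to the P.I. No additional treatments or alteration of concomitant medication schedules will be necessary". Reporting of other medicines is not requested.

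**Analysis.** Section 11 states: "Pairwise t-tests will be used to assess significance among pre- vs. post-prebiotic elimination rates". It names no covariate or sensitivity analysis for this comparison.

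**The concern.** Every subject takes the prebiotic in Trial 2 and none in Trial 1, so each subject is their own only control. The comparison is more credible if it can be shown that little else changed. That requires the same facts, over the same look-back, on both sides. Here each pre-trial item is known on one side only, so no within-person change in it can be computed.

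Antibiotics matter most. Section 1D says that elimination in one person varies over time and is significantly slower on antibiotics, and the entry exclusion treats recent use as relevant. Trial 1 therefore starts from a screened state. Trial 2 may follow a recent course with no required record of it. If such a course still slowed elimination, the effect would run in one direction, towards slower elimination in Trial 2, and could hide or offset a prebiotic effect. The analyst could not find the affected pairs.

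**Working it through.** **1. Coverage, side by side.**

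| Item | Before Trial 1 | Within Trial 1 | Before Trial 2 (washout) | Within Trial 2 |
|---|---|---|---|---|
| Antibiotics | Yes (3B, 4A) | Elimination period (6) | Not asked | Elimination period (6) |
| Other medicines | Yes, initial visit (5C) | Not updated | Not asked | Not asked |
| Fish/seafood | Not asked | Diary | Yes, recalled (5C) | Diary |
| Illness, stress | Not asked beyond self-reported good health (3B) | Diary | Yes, recalled (5C) | Diary |

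A smaller asymmetry appears in Appendix 1: the diary starts at day 0 in Trial 1 and at day -7 in Trial 2.

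**2. Age of the medication list.** The inputs are Trial 1 day 74, a 4-month washout (taken as 120 days, an assumption) and a Trial 2 start at day -7 (Appendix 1). The initial visit is taken as Trial 1 day 0. It can be earlier, so these are minimum ages.

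- At Trial 2 day 0: 74 + 120 + 7 = 201 days.
- At the Trial 2 hair sample: 201 + 74 = 275 days.

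**3. Does prior fish intake bias the slope?** Section 5C fits a straight line to log mercury over time. With first-order elimination at rate k, mercury left from earlier fish (A) and from the study meals (M) decline together: C(t) = (A + M)e^(-kt), so ln C = ln(A + M) - kt. A changes the intercept and leaves the slope at -k. Under the plan's own model, prior fish need not bias the elimination rate. It could blur the meal peaks, 14 days apart, that calibrate each hair's growth rate. Fish is therefore the weaker part of the concern.

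**4. The plan's own figure.** The plan gives no figure on this point. Section 11's power statement is for a correlation: R² = 0.19, so r = 0.436. With 40 subjects and two-sided 0.05 (assumed, as no alpha is given), power = Φ(atanh(0.436) × √37 - 1.96) = 81%. The stated figure of at least 80% reproduces, but it does not bear on the paired comparison.

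**5. What an unrecorded shift could do (illustration only).** If a share p of pairs moves by d in the same direction, the mean paired difference moves by p × d. Changes in mixed directions mainly add noise. Let δ be the mean shift in SDs of the paired differences. With 40 pairs, no true prebiotic effect and two-sided 0.05, the t statistic is noncentral t with 39 degrees of freedom and noncentrality δ√40:

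| δ (assumed) | Noncentrality | Chance of a significant result |
|---|---|---|
| 0.1 | 0.63 | 9% |
| 0.2 | 1.26 | 23% |
| 0.3 | 1.90 | 46% |
| 0.5 | 3.16 | 87% |

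The documents give no p, no d and no SD of the paired differences. The table shows how sensitive the test is; it does not estimate the bias.

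**The case against.** A reader might infer that, because of the one-sided questions, a between-trial difference in any of these factors is indistinguishable from a prebiotic effect. The documents do not support that, for four reasons.

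- **Within-trial records are symmetric.** Food, illness and stress are recorded in both trials, fish is barred for the 60 days over which the rate is estimated, and antibiotics in that period are reportable. This stands, and it limits the gap to the pre-trial periods and non-antibiotic medicines in Trial 2.
- **Stool is a partial check on drift.** Samples at Trial 1 day 44 and Trial 2 day -7 lie about 30 + 120 = 150 days apart, and the second precedes or coincides with the start of prebiotic. A change in the microbiota over the washout would be partly visible. Its cause would not be, and without a medication record the disturbed pairs cannot be identified.
- **Hair may show some background.** A segment of 3.0 to 3.3 cm at 1.1 cm per month (30.4 days) spans about 83 to 91 days, so roughly 9 to 17 days before the first meal in each trial. The plan does not commit to using it this way.
- **The root problem is the fixed order without a control.** Period and prebiotic coincide for everyone, and a matched form would not change that. This stands in full.

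The washout illness question may also bring out an antibiotic course by chance, but nothing requires it to be recorded.

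**Conclusion.** The asymmetry is in the text, and no other section supplies the missing half. The part that matters most is the absence of any question on antibiotics or changed medicines in the washout, given the protocol's own statement that antibiotics slow elimination. That statement concerns elimination while taking them; an effect persisting from a washout course is an assumption, though one consistent with the two-month entry exclusion. Missing fish, illness and stress history before Trial 1 is secondary.

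The size of any bias cannot be computed from the documents. It would also be wrong to infer that matching the questions would make the comparison causal. Matched data allow description, partial adjustment and a check in undisturbed pairs, and nothing more. This is a worthwhile, inexpensive improvement in data collection, not a flaw that invalidates the comparison.

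**What to change.** 1. **Section 5C and Appendix 1:** use one identical short form at both mandatory start-of-trial visits. It should cover all current medicines, antibiotic use, fish/seafood frequency, illness and stress, each over the same look-back. Sections 3B and 6 use two months for antibiotics and the Section 4A phone screen uses one; these passages must be reconciled.
2. **Hair visits:** ask at each one about medicines started or stopped since the form.
3. **Section 11:** keep the paired comparison in all subjects as the main analysis. Add a prespecified sensitivity analysis in pairs with no antibiotic use or medication change before or during either trial. Report pre-trial fish frequency, illness and stress descriptively for both trials.
4. **Interpretation:** state that these steps describe and partly adjust for between-trial differences but do not remove the confounding of period with prebiotic.

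The cost is a few minutes at visits that already take place, one form, minor data entry and one extra analysis, which will have fewer than 40 pairs if any are disturbed. The form should be in place before enrolment, because pre-Trial 1 history is hard to recover reliably later.

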- Subjects must be in good general health based on self-reported health status, with the exception of self-reported conditions listed in the exclusion criteria.
- Subject must be willing to comply with study procedures.

Exclusion Criteria:

- Known allergy to fish.
- Pregnant or lactating women.
- Use of hair dyes or chemical treatments within the prior month and/or intent to use such treatments during the two trial periods. (Hair treatment during the washout period up to one month prior to the second trial is acceptable).
- Known gastrointestinal or renal disorders.
- Subjects with diminished mental capacity.
- Use of antibiotics within two months leading up to the study.

3C. Discussion of Subject Population

The inclusion criteria are very broad and it is anticipated a large diversity in age and ethnicity will result. This is acceptable as age and ethnicity, although not primary study objectives in this pilot, are likely to produce variation in MeHg metabolism and elimination status, the determination of which is an objective of the study. Exclusion criteria are defined based on factors that are likely to result in either harm to the subject or to substantially alter the metabolic processes or analytical procedures of MeHg and thus obscure results. Of particular concern is exposure to the fetus or infant to MeHg, which is known to target the developing nervous system. This concern warrants exclusion of pregnant or breast-feeding women.

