4. SUBJECT IDENTIFICATION, RECRUITMENT, CONSENT AND COMMUNICATION

4A. Method of Subject Identification and Recruitment

Subjects will be recruited through local advertising by posting RSRB-approved flyers around the University of Rochester Medical Center. Response via phone and email to these postings will be anticipated. The P.I. and Lab personnel will also inform friends and acquaintances about the study. Lab personnel will be prepared to tell interested persons of the existence of the study and provide interested persons with contact information for the P.I. for follow up. The Lab personnel will not inquire about health status or other personal information required of interested persons for consent. For phone inquiries the P.I. will perform an initial screening. Potential subjects will be asked if any of the following apply to them:

- Do you have any known allergy to fish?
- Are you pregnant or currently breastfeeding?
- Have you used hair dyes or treatments within the last month?
- Do you have any gastrointestinal or renal (kidney) disorders?
- Have you used antibiotics within the last month?

Subjects answering "no" to all of the above will be asked to follow up with the initial office visit.

Process of Consent

Subjects with Capacity: Only subjects with capacity will be recruited into the study. Subjects with capacity will be consented by the P.I. or study coordinator (TBD) listed on the protocol. The consent form will be reviewed with the subject directly, and the subject will also be offered the opportunity to review the consent form on their own. They will be encouraged to ask any questions and will be free to choose whether or not to participate.

Subject Comprehension: All subjects will be asked, in a private setting, if they understand all aspects of the consent form and expectations of participation in the protocol. They will be provided with contact information for the investigator and encouraged to ask for clarification at any time. Reading skills will be assessed by asking all participants, in private, if they would like any assistance in reading forms.

Documentation of Consent. All subjects will receive a signed copy of the consent form, and all consent forms will be kept on file in a locked office [name].

Costs to Subjects. There will be no costs incurred by subjects participating in the study.

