5. METHODS AND STUDY PROCEDURES

5A. Overview:

The study will follow the protocol outlined below under “specific methods”. A timeline of study activities can be seen in Figure 1 and Appendix 1. The study will engage human subjects in six activities to execute this protocol: 1) recruitment, 2) collection of body metrics (weight, height) and oral observation for presence/absence of amalgam fillings, 3) fish meal consumption 4) fecal sample collection and submission and 5) hair sample collection, 6) prebiotic self-administration (see below). A total of four visits will be mandatory, one at the beginning and one at the end of each trial. Fecal sample submission will be done with a shipping protocol, or scheduled pick up by lab staff, and will not require a visit. Steps 2-4 above are anticipated to occur over a period of approximately 74 days (see Figure 1 and Appendix 1). Step 5 will commence one week prior to the first fish meal in the second trial (Figure 1). Subjects will be asked to keep a food diary in a provided notebook and include notes on their general health, and particularly any illness or unusual diet habits, over the study period. The entire study, including pre-study preparations, subject enrollment, two trials of fish meal administration and hair and feces sampling, Hg measurements, microbiome analysis and statistical analysis of the data is anticipated to take place over a period of three years.

5B. Approach.

Our approach is summarized schematically in Figure 1. Subjects will consume three meals of tuna steaks, each meal separated by seven days (on days 0, 7 and 14”). This will be followed by an elimination period of 60 days where subjects will resume normal daily diets and activities. Hair will be sampled on or near the 60th day after the last fish meal. Fecal samples will be taken at three time points: one each within 30 days following the last fish meal for each trial and one prior to, or upon the day of initiating the prebiotic administration in the second trial. Longitudinal Hg analysis of single hair strands will be performed with LA-ICP-MS. iHg and MeHg levels will be determined in fecal samples using tetra-ethylborate (NaBEt₄) derivatization and GC-ICP-MS methods.

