8. SAFETY AND REPORTABLE EVENTS

At the first visit, subjects will be alerted to self-monitor for any adverse event and to contact study staff by phone or email with any concerns. To monitor subject adverse events, study staff will also contact subjects with a phone call or email within the week subsequent to the last fish meal in each Trial (e.g. between days 15-21 of the Trial). An additional call will be made on day "0" of Trial 2 to monitor effects of prebiotic self-administration. Study staff will not call subjects to monitor adverse events during the intermediate 4-month washout period. The most likely causes for an adverse event would be a reaction to consumption of tuna or the prebiotic administered in the second trial. Subjects will be advised to contact the P.I. by phone or email in the instance that an adverse symptom, sign, illness or experience is encountered. In the instance that this occurs before all tuna meals or prebiotic are consumed, the subject will be advised

to refrain from further fish or prebiotic consumption. Adverse events or problems are not expected but will be reported to the RSRB according to OHSP Policy 801 guidelines.

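### No visible step repeats the pregnancy and breastfeeding question before the second set of three tuna meals, roughly six months or more after the first

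*Combined protocol and SAP*

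**What the plan says.** Section 3B lists pregnancy and lactation among the exclusions, with no time limit. Section 3C gives the reason: "Of particular concern is exposure to the fetus or infant to MeHg, which is known to target the developing nervous system". Section 9A repeats the exclusion.

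Section 4A has the P.I. screen phone inquiries with five questions, one of which is "Are you pregnant or currently breastfeeding".

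Section 5A sets the visits: "A total of four visits will be mandatory, one at the beginning and one at the end of each trial". Under Fish meal administration, Section 5C says that "Just prior to each trial, individually weighed, wrapped and frozen portions of tuna steaks" are prepared, so the second set is a separate dispensing. The food and health diary text states which questions about the washout are put to each participant: "at the visit prior to Trial 2, will be asked to comment on fish/seafood eating frequency and if illness or undue stress was experienced".

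For the first visit, Section 8 provides: "subjects will be alerted to self-monitor for any adverse event and to contact study staff by phone or email with any concerns". It also says that staff make no adverse event calls in the washout.

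**The concern.** Pregnancy and breastfeeding change with time. One negative answer before Trial 1 does not establish a woman's status when the exposure is given again after a long gap in which staff do not call her. If the visible plan is followed as written, a woman who became pregnant or began breastfeeding after the phone screen could be handed three portions of tuna that the protocol bars her from eating. The harm at stake is the one that Section 3C singles out. The study plans to consent 23 women aged 18 to 80, to obtain data on 20.

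**Working it through.** **Interval between exposures.** The protocol's own figure reproduces: last fish meal on day 14 plus 60 days of elimination gives day 74, the hair-sampling day in Section 5C.

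- Trial 1 day 0 to day 74: 74 / 30.4 = 2.4 months.
- Washout (Section 2A): 4 months, or 16 weeks (112 / 30.4 = 3.7 months) if a month is read as four weeks.
- First meal of Trial 1 to first meal of Trial 2: 2.4 + 3.7 = 6.1 months, or 2.4 + 4 = 6.4 months. The one-week prebiotic lead-in may add to this.
- If Section 2A's span of approximately 10 months is taken literally: 10 - 2.4 = 7.6 months.

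The text does not fix an exact number of days, so roughly six months or more is as precise as it allows. The phone screen comes before Trial 1 day 0, so the time since the question was asked is longer still.

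**Where a repeat question could sit.** The visible places are:

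| Place | What it covers |
|---|---|
| 4A, phone screen | Asks about pregnancy and breastfeeding, before enrolment |
| 5C, initial visit | Age, sex, body weight, amalgams, current medications |
| 5C, food and health diary, visit before Trial 2 | Fish and seafood frequency, illness, undue stress |
| 7, withdrawals | Withdrawal without consent for non-compliance or loss of funding |
| 8, staff calls | One after the last meal in each trial, one on Trial 2 day 0 about the prebiotic; none in the washout |
| Appendix 1 | Eligibility marked once, before Trial 1 day 0; no pregnancy row |

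Only the first asks the question, and it is asked once. Appendix 1 carries little weight here, for the reason given in the objection. The finding rests on the other entries taken together.

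**The protocol already looks ahead to Trial 2 for one criterion.** Section 3B says of hair treatment: "Hair treatment during the washout period up to one month prior to the second trial is acceptable". At least one eligibility condition is therefore meant to be met afresh at the second trial, although no visible step asks about it then either.

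**The case against.** The case on the other side has five parts.

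1. **Appendix 1 is not an exhaustive schedule.** Providing fish meals is also marked only once, before Trial 1, yet Section 5C has portions prepared before each trial. A single eligibility mark therefore does not prove that eligibility is never confirmed again. This stands, and the mark is weak evidence.

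2. **The pre-Trial 2 list may not be the whole visit.** It sits in the diary text and gathers washout information in place of a diary. This also stands. What remains is that no other visible section supplies the question.

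3. **Some sources cannot be seen.** The consent pages were removed and may tell women to report a pregnancy. Figure 1, which shows the timeline, is missing. This limits the point to the visible text. An instruction given before Trial 1 would still leave detection to the subject and would not be a scheduled check.

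4. **The subject can call.** Appendix 1 keeps ad hoc contact open throughout, including the washout. Section 8, however, frames that contact around adverse events and concerns. A woman would have to recognise that pregnancy matters and volunteer it.

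5. **The dose is capped.** Sections 9A and 9B size portions so that the EPA reference dose, which includes a safety factor of 10, is not exceeded. This limits the possible harm. The protocol nevertheless excludes pregnant and breastfeeding women with that cap in place, so the cap does not replace the check.

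A reader might go further and infer that the protocol permits dosing a pregnant woman in Trial 2. It does not: the exclusion has no end date, and only the visible check is missing.

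**Conclusion.** The point holds as a cheap patient-safety improvement. A single screen cannot enforce a time-varying exclusion across two separate exposures, and no visible passage re-asks the question before the second one, roughly six months or more later.

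The size cannot be stated as an expected number of women, because the documents give nothing from which to derive a pregnancy rate among the 20 to 23 women planned. Possible exposure is limited by the reference-dose cap. Blood concentrations calculated for one assumed tuna mercury level and portion size would describe the dose any subject receives. They would not measure the effect of the missing question, so none is offered.

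A reader might also infer that antibiotic use in the washout breaches eligibility or biases the pre/post-prebiotic comparison. The documents do not support that. Section 3B's criterion concerns "Use of antibiotics within two months leading up to the study", Section 6 permits antibiotics during the elimination period if reported, and nothing shows an effect of a course that ended before Trial 2.

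The conclusion assumes that the unseen consent pages and Figure 1 do not schedule a repeat question. If either does, the remaining step is to bring Section 5C and Appendix 1 into line with it.

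**What to change.** At the existing mandatory visit that begins Trial 2, before tuna is dispensed, ask the Section 4A pregnancy and breastfeeding question again and record the answer. Withhold tuna from anyone who answers yes, and keep her Trial 1 data. In Appendix 1, add an eligibility re-check mark at Trial 2 day -7. Section 3B's one-month hair-treatment rule for Trial 2 can be checked at the same time.

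The cost is a few minutes per subject at a visit that already takes place, one mark in the schedule, and possibly slightly fewer pairs for the pre/post-prebiotic comparison. Section 7 already provides for replacing withdrawn subjects. Self-report can still miss a very early pregnancy, the same limit as at Trial 1.
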